6.9.2.1 Subgroup Analyses

TEAEs will also be summarized by atrial fibrillation status and by baseline peak VO₂ (<60% or ≥60%), respectively, with the number and percentage of subjects by SOC and PT. Subgroup analyses will be performed only if the total number of subjects in each treatment group within a subgroup category is >10.

6.9.2.2 TEAEs of Clinical Interest (AECI)

Although not collected as such in the protocol, based on a possible class effect with sGC stimulators, TEAEs related to bleeding, hypotension, and elevated heart rate will be categorized as AECI. These will be summarized by treatment group, by severity and by PT and presented in

a by-patient listing. See Appendix 1 for details on the determination of the events for each category of interest.

6.9.3 Clinical Laboratory Endpoints

For each quantitative clinical laboratory endpoint, descriptive statistics of the observed values (in standard units) as well as change from study baseline will be presented overall for each assessment timepoint for the Safety Population. 95% confidence intervals for the change from baseline endpoints will also be presented.

Laboratory test values will also be categorized as low, normal, or high based on reference ranges provided by the lab. Shifts from study baseline to each later timepoint will be tabulated. If there is more than 1 measurement for a lab parameter at a postbaseline timepoint, only the last measurement will be used. Listings of laboratory endpoints with reference ranges and the above categorizations will be provided.

Clinical laboratory test values will also be considered potentially clinically significant (PCS) if they meet either the lower-limit or higher-limit PCS criteria listed in Table 5. The number and percentage of patients who have PCS post-baseline clinical laboratory values will be tabulated by treatment group. The percentages will be calculated relative to the number of patients with available non-PCS baseline values and at least 1 assessment in the corresponding postbaseline period. The numerator will be the total number of patients with available non-PCS baseline values and at least 1 PCS value in the corresponding postbaseline period. A supportive listing of patients with PCS postbaseline values will be provided, including the baseline and all postbaseline (including non-PCS) values. A listing of all TEAEs for patients with postbaseline PCS laboratory values will also be provided.

Table 5. Criteria for Potentially Clinically Significant Laboratory Results

Parameter	SI Unit	Lower Limit	Higher Limit
CHEMISTRY			
Albumin	g/L	< 0.75 × LLN	> 1.1 × ULN

Table 5. Criteria for Potentially Clinically Significant Laboratory Results

Alanine aminotransferase	U/L	—	$\geq 3 \times \text{ULN}$
Alkaline phosphatase	U/L	—	$\geq 3 \times \text{ULN}$
Aspartate aminotransferase	U/L	—	$\geq 3 \times \text{ULN}$
Bicarbonate	mmol/L	$< 0.9 \times \text{LLN}$	$> 1.1 \times \text{ULN}$
Bilirubin, total	$\mu\text{mol/L}$	—	$> 1.5 \times \text{ULN}$
Calcium	mmol/L	$< 0.9 \times \text{LLN}$	$> 1.1 \times \text{ULN}$
Chloride	mmol/L	$< 0.9 \times \text{LLN}$	$> 1.1 \times \text{ULN}$
Cholesterol, total	mmol/L	—	$> 1.6 \times \text{ULN}$
Creatinine	$\mu\text{mol/L}$	—	$> 1.3 \times \text{ULN}$
Glucose	mmol/L	$< 0.8 \times \text{LLN}$	$> 1.4 \times \text{ULN}$
Phosphate	mmol/L	$< 0.9 \times \text{LLN}$	$> 1.1 \times \text{ULN}$
Potassium	mmol/L	$< 0.9 \times \text{LLN}$	$> 1.1 \times \text{ULN}$
Protein, total	g/L	$< 0.9 \times \text{LLN}$	$> 1.1 \times \text{ULN}$
Sodium	mmol/L	$< 0.9 \times \text{LLN}$	$> 1.1 \times \text{ULN}$
Uric acid	$\mu\text{mol/L}$	$< 0.9 \times \text{LLN}$	$> 1.1 \times \text{ULN}$
HEMATOLOGY			
Hematocrit	Ratio	$< 0.8 \times \text{LLN}$	$> 1.1 \times \text{ULN}$
Hemoglobin	g/L	$< 0.8 \times \text{LLN}$	$> 1.1 \times \text{ULN}$
Neutrophils, absolute cell count	$10^9/\text{L}$	$< 0.8 \times \text{LLN}$	$> 1.5 \times \text{ULN}$
Platelet count	$10^9/\text{L}$	$< 0.5 \times \text{LLN}$	$> 1.5 \times \text{ULN}$
Red blood cell count	$10^{12}/\text{L}$	$< 0.8 \times \text{LLN}$	$> 1.1 \times \text{ULN}$
White blood cell count	$10^9/\text{L}$	$< 0.7 \times \text{LLN}$	$> 1.5 \times \text{ULN}$

LLN = lower limit of normal value provided by the laboratory; SI = *Le Système International d'Unités* (International System of Units); ULN = upper limit of normal value provided by the laboratory.

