3. Patient has had coronary artery bypass graft, cardiac mechanical support implantation, or other cardiac surgery in the 3 months before the Screening Visit or planned during the study.
4. Patient has severe chronic obstructive pulmonary disease (COPD) as defined by chronic oxygen dependence. Nighttime oxygen is not exclusionary.
5. Patient had had heart failure hospitalization with discharge within 30 days before the Baseline Visit.
6. Patient has hypertrophic cardiomyopathy (obstructive or nonobstructive), restrictive cardiomyopathy, active myocarditis, constrictive pericarditis, cardiac sarcoidosis, or known amyloid cardiomyopathy.
7. Patient has uncontrolled arrhythmias other than permanent or persistent atrial fibrillation.
8. Patient has history of uncorrected congenital cardiac disease affecting LV function.
9. Patient has evidence of severe chronotropic incompetence, as indicated by a heart rate response $<55\%$ of predicted maximum heart rate ($220 - \text{age}$) per Baseline Visit CPET.
10. Patient has any history of platelet dysfunction, hemophilia, von Willebrand disease, coagulation disorder causing a bleeding diathesis, other bleeding diathesis, or significant, nontraumatic bleeding episodes, such as from a gastrointestinal source.

11. Patient has uncorrected thyroid disease.
12. Patient has severe aortic stenosis or severe mitral regurgitation.
13. Patient has seated systolic BP <110 mmHg at the Screening Visit and on Day 1 before Randomization. For these determinations of eligibility, BP will be the average of 3 measurements obtained at approximately 2-minute intervals after the patient has been sitting quietly for ≥ 5 minutes.
14. Patient has estimated glomerular filtration rate (eGFR) <30 mL/min/1.73m² at the Screening Visit and/or is receiving dialysis.
15. Patient has direct bilirubin >2 times upper limit of normal (\times ULN, as defined by laboratory) or alanine aminotransferase (ALT) or aspartate aminotransferase (AST) >3 \times ULN at the Screening Visit.
16. Patient has received IV inotropic therapy within 30 days before the Screening Visit.
17. Patient is unable to take oral medications.
18. Patient has active or treated malignancies within 12 months of the Screening Visit, except for basal cell carcinoma.

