3.8.8.5 Estimated Glomerular Filtration Rate

Estimated glomerular filtration rate (eGFR) will be based on the serum creatinine level determined as part of the clinical laboratory tests ([Table 7](#)) and will be calculated according to the Chronic Kidney Disease Epidemiology Collaboration (CKD-EPI) creatinine equation.[\(29\)](#)

The CKD-EPI equation, expressed as a single equation, is

$$\text{GFR} = 141 \times \min(\text{Scr}/\kappa, 1)^\alpha \times \max(\text{Scr}/\kappa, 1)^{-1.209} \times 0.993^{\text{Age}} \times 1.018 \text{ [if female]} \times 1.159 \text{ [if black]}$$

where Scr is serum creatinine, κ is 0.7 for females and 0.9 for males, α is -0.329 for females and -0.411 for males, min indicates the minimum of Scr/ κ or 1, and max indicates the maximum of Scr/ κ or 1.

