5.3 DEFINITION OF BASELINE

The following definition of baseline will be used, unless specified otherwise:

- Study baseline will be defined as the last non-missing assessment before first administration of study drug, usually the predose assessment on Day 1

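### Patients who start above the creatinine flag (1.3 x ULN) cannot show further renal worsening in either laboratory frequency table of SAP 6.9.3; one row relative to own baseline would close the gap.

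*SAP*

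**What the plan says.** SAP 6.9.3 plans two categorical laboratory displays.

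- **PCS table.** On the denominator: "The percentages will be calculated relative to the number of patients with available non-PCS baseline values", with at least one postbaseline assessment. On the numerator: "The numerator will be the total number of patients with available non-PCS baseline values and at least 1 PCS value". Table 5 gives creatinine one criterion, above 1.3 x ULN, where "ULN = upper limit of normal value provided by the laboratory". There is no eGFR or BUN row, and no criterion in Table 5 refers to the patient's own baseline.
- **Shift table.** "Laboratory test values will also be categorized as low, normal, or high based on reference ranges provided by the lab". There are no grades above the upper limit.

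SAP 5.3 fixes the baseline: "Study baseline will be defined as the last non-missing assessment before first administration of study drug".

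The renal entry limit is Protocol Exclusion Criterion 14, which excludes on "Patient has estimated glomerular filtration rate (eGFR) <30" at the Screening Visit, or on dialysis. Protocol 3.8.8.5 computes eGFR by the CKD-EPI creatinine equation.

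The plan has other laboratory outputs. SAP 6.9.3 gives descriptive statistics for change from baseline with 95% confidence intervals, a listing of patients with postbaseline PCS values, and a listing of the TEAEs in those patients. Protocol 3.8.13.4 makes a laboratory abnormality an adverse event if the investigator judges it clinically significant or it needs intervention.

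**The concern.** Leaving out patients who are abnormal at baseline is a sensible way to count newly emergent abnormalities. It works if some other display shows worsening in those left out. For creatinine, the only other categorical display has a single category above normal, so a stable patient and one whose creatinine doubles look the same.

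The patients affected are those admitted with the least renal reserve. SAP 6.9.2.2 names hypotension as a possible class effect, and Protocol 1.3.1.1 reports dose-dependent blood pressure lowering in a rat model. Safety is a primary objective, and renal events are not among the categories of clinical interest in SAP Appendix 1. An imbalance between arms confined to these patients would have no row in which to appear as a count.

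**Working it through.** The plan states no figure on this point, so there is none to reproduce. The check asks whether patients whom Exclusion 14 admits lie above the creatinine flag, and up to what eGFR.

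**Inputs**
- Flag: creatinine above 1.3 x ULN (SAP Table 5).
- Entry limit: eGFR 30 (Protocol Exclusion 14).
- Equation (Protocol 3.8.8.5): eGFR = 141 x min(Scr/κ, 1)^α x max(Scr/κ, 1)^-1.209 x 0.993^age x 1.018 if female x 1.159 if black; "where Scr is serum creatinine, κ is 0.7 for females and 0.9 for males".
- ULN: not in the documents. Assumed 1.10-1.35 mg/dL for men and 0.90-1.20 mg/dL for women.
- Age 70 as the reference, with 0.993^70 = 0.6116. The 1.159 factor is left out at first.

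**Step 1: eGFR at the flag.** At 1.3 x ULN creatinine exceeds κ throughout, so the min term is 1.
- Men, ULN 1.10: Scr = 1.43; 141 x (1.43/0.9)^-1.209 x 0.6116 = 49.3.
- Men, ULN 1.20: Scr = 1.56; eGFR 44.3.
- Men, ULN 1.35: Scr = 1.755; eGFR 38.5.
- Women, ULN 0.90: Scr = 1.17; 141 x (1.17/0.7)^-1.209 x 0.6116 x 1.018 = 47.2.
- Women, ULN 1.00: Scr = 1.30; eGFR 41.5.
- Women, ULN 1.20: Scr = 1.56; eGFR 33.3.

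Over ages 45 to 85 and the same ULNs, the flag lies at an eGFR of about 30 to 59. With the 1.159 factor it lies at about 35 to 68.

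**Step 2: creatinine at the entry limit.** Inverting the equation at age 70, eGFR 30 corresponds to 2.16 mg/dL in men (1.60-1.96 x ULN) and 1.70 mg/dL in women (1.42-1.89 x ULN). All are above 1.3 x ULN. A 70-year-old with a baseline eGFR of 30 is therefore out of the creatinine PCS row under every ULN assumed.

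**Step 3: creatinine at eGFR 45.** At age 70 this is 1.54 mg/dL in men (1.14-1.40 x ULN) and 1.22 mg/dL in women (1.01-1.35 x ULN). Many combinations fall below the flag. Those patients stay in the PCS row and count if they later cross it.

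**Step 4: one patient followed through.** A man aged 70 with ULN 1.20 mg/dL and eGFR 40 has creatinine 1.70 mg/dL, or 1.42 x ULN. Below normal function eGFR scales as the creatinine ratio to the power -1.209.
- A 1.5-fold rise gives 40 x 1.5^-1.209 = 40 x 0.612 = 24.5.
- A doubling gives 40 x 2^-1.209 = 40 x 0.433 = 17.3.

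In both cases he is absent from the creatinine PCS row and is high to high in the shift table.

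**The case against.** The strongest reply is that the worsening is not lost, and most of that reply stands.

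- TEAEs are tabulated by arm for the whole Safety Population, whatever the baseline laboratory value, and they are the primary safety endpoint. A renal decline that the investigator judges significant enters there. The limit is that entry depends on that judgement.
- The continuous summaries are more than a mean. SAP 5.1 adds the median, quartiles, minimum and maximum, so a doubled creatinine would influence the extreme of the change distribution. SAP 6.9.3 describes this summary as overall, but Protocol 5.10.2 and the general rule in SAP 5.1 set it by treatment group. These statistics still give no count of patients who worsened.
- The two PCS listings are not confined to patients with a non-PCS baseline. They show individual values, not a comparison of arms.
- Counting only new abnormalities is a uniform convention, used also for vital signs and ECG, and is reasonable in a descriptive phase 2 trial.

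Four stronger readings are tempting, and the documents do not support them.

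- *That renal function goes unanalysed.* Much of SAP 6.8.4 and parts of SAP 7 are blacked out, and the SAP reference list holds the eGFR equation paper although no visible text cites it. An eGFR analysis may exist there.
- *That the hidden band is eGFR 30 to a fixed figure such as 45.* The upper end depends on a ULN that is not given, and on age, sex and the 1.159 factor.
- *That many patients are affected.* No baseline eGFR distribution is given. The trial enrols patients with heart failure and excludes an eGFR below 30; it does not select for renal impairment. The only renal findings in the protocol are nonclinical and favourable.
- *That these patients vanish from the laboratory tables.* They are in the shift table, where only their further rise is invisible. The PCS exclusion also appears to act parameter by parameter, so they can still count for potassium and other rows.

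**Conclusion.** The point holds in a limited form. For patients whose baseline creatinine exceeds 1.3 x ULN, neither laboratory frequency table in SAP 6.9.3 can show a further rise, and no visible objective frequency by arm captures it elsewhere.

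Under the assumed ULNs, at age 70 and without the 1.159 factor, this covers patients from an eGFR of 30 up to about 38-49 in men and 33-47 in women. Because eligibility uses the screening value and the PCS flag uses the last predose value, 30 is not a strict floor at baseline. The number of patients affected cannot be derived from the documents and may be small.

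No efficacy result and no primary safety endpoint changes. This is a worthwhile, inexpensive improvement to a safety display. It does not show that the safety analysis is invalid.

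**What to change.** Keep the existing Table 5 rows and the convention of counting treatment-emergent abnormalities. Add one renal row defined against the patient's own baseline, for example creatinine at least 1.5 x baseline, or an eGFR fall of at least 30%. Tabulate it by treatment group for all Safety patients with a baseline and at least one postbaseline value, including those already above 1.3 x ULN at baseline.

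The two examples are not equivalent. By the exponent in the protocol's equation, for creatinine above κ, a 30% fall in eGFR is a creatinine ratio of 0.7^(-1/1.209) = 1.34, whereas a ratio of 1.5 is a fall of about 39% (1 - 0.612). The sponsor should choose one reporting threshold and confirm it before unblinding.

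The pattern is already in the plan: the weight rows of SAP Table 6 use change from baseline alone. Serum chemistry is scheduled at every visit, so no new data are needed. If a redacted section already holds such a tabulation for the Safety Population by arm, a cross-reference from SAP 6.9.3 would do. The cost is one more descriptive safety frequency to interpret.

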6.9.4 Vital Signs Endpoints

Descriptive statistics of the observed values as well as change from study baseline will be presented for seated BP and pulse at each assessment timepoint for the Safety Population. 95%

confidence intervals for the change from baseline endpoints will also be presented. Vital signs evaluations at each assessment timepoint will be presented in a by-patient listing.

The number and percentage of patients who had a PCS change from study baseline in BP and pulse (based on the criteria in Table 6), will be presented by treatment group. Percentages will be calculated relative to the number of patients with available non-PCS baseline values and at least 1 assessment in the corresponding postbaseline period. The numerator will be the total number of patients with available non-PCS baseline values and at least 1 PCS value in the corresponding postbaseline period.

Table 6. Criteria for Potentially Clinically Significant Vital Signs Results

Vital Sign Parameter	Flag	Criteria*	
		Observed Value	Change from Study Baseline
Seated Systolic Blood Pressure (mmHg)	High	≥ 180	Increase of ≥ 30
	Low	≤ 90	Decrease of ≥ 30
Seated Diastolic Blood Pressure (mmHg)	High	≥ 105	Increase of ≥ 20
Seated Pulse Rate (bpm)	High	≥ 110	Increase of ≥ 20
	Low	≤ 50	Decrease of ≥ 20
Weight, kg	High	—	Increase of > 5 kg and ≥ 5%
	Low	—	Decrease of > 5 kg and ≥ 5%

*A postbaseline value is considered potentially clinically significant if it meets both the criteria for observed value and change from baseline.

Orthostatic changes in systolic BP, diastolic BP, and pulse will be summarized for each treatment group. An orthostatic measurement is obtained by subtracting the seated measurement from the standing measurement.

The number and percentage of patients who meet the following notable orthostatic criteria at any postdose timepoint during a visit, as well as over the overall treatment period will also be summarized by treatment group:

- Orthostatic decrease in systolic BP of > 20 mmHg from seated to standing
- Orthostatic increase in pulse of > 30 bpm from seated to standing

A supportive listing of patients with PCS postbaseline values or notable orthostatic values will be provided, including the baseline and all postbaseline (including non-PCS) values. A listing of all TEAEs for patients with postbaseline PCS vital signs values will also be provided.

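### The joint low-systolic flag in SAP Table 6 leaves some seated readings at or below 90 mmHg out of the by-arm count when baseline is below 120 mmHg; one extra row closes the gap

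*SAP*

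**What the plan says.** SAP section 6.9.4 plans a count by treatment group: "The number and percentage of patients who had a PCS change from study baseline in BP and pulse". Table 6 sets the limits. For low seated systolic pressure they are an observed value of 90 mmHg or less and a change from study baseline given as "Decrease of ≥ 30". The footnote joins them: "A postbaseline value is considered potentially clinically significant if it meets both the criteria for observed value and change from baseline". The same flag feeds two listings, a supportive listing of patients with flagged values (or notable orthostatic values) and a listing of all TEAEs in patients with flagged vital signs.

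The baseline is set in SAP section 5.3: "Study baseline will be defined as the last non-missing assessment before first administration of study drug", usually the Day 1 predose value. The entry limit is Protocol exclusion criterion 13: "Patient has seated systolic BP <110 mmHg at the Screening Visit and on Day 1 before Randomization". A patient at exactly 110 mmHg is therefore admitted.

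Hypotension is named as a possible class effect in SAP section 6.9.2.2: "TEAEs related to bleeding, hypotension, and elevated heart rate will be categorized as AECI".

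Section 6.9.4 also reports seated pressure outside the flag. It gives descriptive statistics of observed values and changes at each timepoint with 95% confidence intervals, and it states: "Vital signs evaluations at each assessment timepoint will be presented in a by-patient listing". Under SAP section 5.1 those statistics are by treatment group and include the minimum and the 25th percentile.

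**The concern.** The two halves of the low-systolic flag do not fit the entry limit. A patient who starts at 110 mmHg cannot show a fall of 30 mmHg until the pressure reaches 80, so the limit of 90 mmHg has no effect for that patient. The flag is thus hardest to trigger in patients who start nearest to low pressure. A move from 120 to 90 mmHg is counted, while a move from 112 to 83 mmHg, which ends 7 mmHg lower, is not.

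No other table in the legible SAP counts low seated systolic pressure by arm. The notable orthostatic criteria in section 6.9.4 and the vital-sign column of Table 8 (Appendix 1) concern the change from sitting to standing. The laboratory and ECG flags (sections 6.9.3 and 6.9.5) use the observed value alone, so the joint requirement is not the SAP's general practice.

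What is at stake is how complete one safety count is for an effect that the SAP itself singles out. A reader of that row may take it as the number of patients who reached 90 mmHg or less, and it is not that number.

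**Working it through.** The documents state no figure for this flag, so there is nothing to reproduce. The check is an enumeration in whole mmHg.

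**Inputs**
- Observed-value limit: v ≤ 90 (SAP Table 6).
- Change limit: b − v ≥ 30 (SAP Table 6).
- Both required (footnote to Table 6).
- Baseline b: last value before first dose (SAP 5.3).
- Lowest admitted value: 110 (Protocol exclusion 13).

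**Step 1: effective cut-off.** The flag fires when v ≤ 90 and v ≤ b − 30, that is, when v ≤ min(90, b − 30).

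**Step 2: readings left out.** A reading is 90 or less but not flagged when b − 30 < v ≤ 90, so v runs from b − 29 to 90. For b from 110 to 119 that is 120 − b values; from b = 120 it is none.

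| Baseline b | Flag fires at | Left out | Number of values |
|---|---|---|---|
| 110 | ≤ 80 | 81–90 | 10 |
| 112 | ≤ 82 | 83–90 | 8 |
| 115 | ≤ 85 | 86–90 | 5 |
| 117 | ≤ 87 | 88–90 | 3 |
| 119 | ≤ 89 | 90 | 1 |
| ≥ 120 | ≤ 90 | none | 0 |

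**Step 3: whole block.** Baselines 110–119 and readings 81–90 form 10 × 10 = 100 pairs. Unflagged: 10 + 9 + … + 1 = 55. Flagged: 45. These pairs are not equally likely in practice, so 55 of 100 describes the rule and is not a rate in patients.

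**Step 4: how often (assumption only).** The documents give no blood pressure distribution. Suppose that baseline B is normal with mean m = 125–135 and SD 15, truncated at 110, and that the change is independent of B and normal with mean d = −5 to −8 and SD s = 12–15. Then
- P(v ≤ 90) = E[Φ((90 − B − d)/s)]
- P(flagged) = E[Φ((min(90, B − 30) − B − d)/s)]

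Over this grid:
- 12–25% of patients have a baseline below 120.
- 24–52% of readings at or below 90 are unflagged.
- Unflagged readings are about 0.3–1.4% of all readings at one timepoint.

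At m = 130, d = −5, s = 12, 1.06% of readings are at or below 90 and 0.54% are flagged. With the 92 patients per arm of the Protocol synopsis, 0.3–1.4% is about 0.3–1.3 patients per arm at a single timepoint, and more across repeated readings. If low baselines tend to rise on remeasurement, the figure would be lower.

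**Step 5: contrast between arms (assumption only).** Keep m = 130 and s = 12, and set d = 0 for placebo and d = −5 for active. The joint flag then gives 0.17% against 0.54% of readings (ratio about 3.1, difference 0.37 points). The observed-value limit alone gives 0.40% against 1.06% (ratio about 2.6, difference 0.66 points). The joint rule shrinks the absolute difference and enlarges the ratio.

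**The case against.** The case for leaving Table 6 alone has real force.

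- **Nothing is lost from the data.** Descriptive statistics by arm include the minimum at each timepoint, and every reading is in the by-patient listing. This stands. What is missing is only the patient count by arm and the entry that the flag gives to the two linked listings. A patient may still enter the supportive listing through another criterion.
- **Relevant falls have another route.** Protocol section 3.8.13.4 asks for vital-sign changes to be reported as adverse events if the Investigator considers them clinically significant or they need intervention. SAP Appendix 1 then picks up hypotension terms, with medical review before lock. This stands in part: that route depends on judgement at the site, whereas a numeric count does not.
- **Joint limits can be deliberate.** Requiring a value and a change suppresses trivial flags, the blood pressure and pulse rows of Table 6 all work this way, and the SAP describes the count as one of change from baseline. No document says that these limits must match the entry floor. This stands, and it is why the joint flag should stay.

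Three stronger readings are tempting, and the documents support none of them.

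1. A reader might infer that the rule makes 40 mg look safer. The rule is identical in both arms, and step 5 shows that the effect on the contrast depends on the scale used.
2. A reader might infer that monitoring or stopping is weakened. The DMC trigger and individual stopping criteria (Protocol sections 3.7 to 3.7.2) rest on study drug-related SAEs and do not use Table 6. The primary safety endpoint, TEAE incidence, does not use it either.
3. A reader might infer that every patient entering at 110–119 can reach 81–90 uncounted. That full band is missed only at 110.

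**Conclusion.** The gap is real and follows from the text alone: for baselines below 120 mmHg, seated systolic readings from b − 29 to 90 mmHg stay out of the by-arm count and do not trigger the linked listings. It is at most 10 mmHg wide for a baseline of 110 or more and disappears at 120.

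This takes 110 mmHg as the lowest baseline. Exclusion 13 joins Screening and Day 1 with the word and, so on a literal reading a patient below 110 on Day 1 only is not excluded. The band would then be wider: 76–90 at a baseline of 105, for example.

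The number of patients affected is unknown. The percentages in step 4 rest wholly on assumed distributions and suggest a small absolute number, although it may be a sizeable share of a rare event. No direction of bias between arms is established, and no data are lost. The point is a cheap improvement to the reporting of a named class concern; the sponsor could make it, and the plan is not wrong without it.

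**What to change.** Keep the joint flag and its limits. Add one row to the Table 6 summary: by arm, the number and percentage of patients with any postbaseline seated systolic pressure of 90 mmHg or less, regardless of change. Use the section's existing denominator convention, so that the percentage is based on patients whose baseline is above 90 mmHg and who have at least one postbaseline assessment. Include these patients in the supportive listing and in the linked TEAE listing.

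The row uses a cut-off already in the SAP and needs no new data. The cost is one more row and a few more listed patients, some with minor readings. Counting every fall of 30 mmHg or more on its own is not worth adding: under the step 4 assumptions it would capture about 2–7% of readings, including moves such as 160 to 130 mmHg that say nothing about low pressure.
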